7.2. Schedule of assessments

ASSESSMENT	PERFORMED BY	SCREENING / V0	BASELINE / V1	VISIT 2-7	VISIT 8 / TERMINATION
		DAY 0	DAY 1	DAY 2 TO 7	DAY 8
Review of Subject Information and Consent Form	Investigator	X			
Sign Informed Consent	Investigator	X			
Check of in- and exclusion criteria	Investigator	X	X		
Collect Screening Information	Investigator or delegate	X			
Collect Baseline Information	Investigator or delegate		X		
Partial lift of test product and skin inspection of sacral skin	Investigator or delegate			X	X
Application of Biatain® Silicone Sacral	Investigator or delegate		X		
Dressing inspection	Investigator or delegate			X	
Removal of Biatain® Silicone Sacral	Investigator or delegate				X
Review of AEs/ADEs/SAEs/SADEs	Investigator or delegate		X	X	X
Insurance of subjects' wellbeing and compliance with CIP	Investigator or delegate		X	X	X
Termination form at discharge or V8	Investigator/Subject			(X)	X
eCRF reporting	Investigator	X	X	X	X

Table 5. Visit overview. (Screening V0 and Baseline V1 can be performed the same day).

7.3. Case Report Forms

All assessments and observations throughout the investigation for each subject must be carefully recorded in an electronic CRF (eCRF) or in a paper CRF.

CRFs will be completed by the investigator and/or delegated site personal, who have signed the Site Personnel Signature and Delegation List and Clinical Investigation Training Log.

An eCRF is provided for each subject. It is the responsibility of the Investigator that all data are entered promptly and correctly.

7.4. Concomitant treatment

Concomitant medication taken from the time of consent through the investigation until termination will be registered in the eCRF in the concomitant section.

Any changes in medicine during the test period must be reported in the concomitant section in the eCRF.

Topical treatment with steroid cream in the sacral area within the past 14 days or during the investigation is an exclusion criterion.

7.5. Supplementary materials and equipment (if applicable)

The investigation product is applied on the subject by the site personnel and will not be handed out to the subject. The investigational products will be stored at the site.

Sponsor will provide the PI, or delegate with supplementary materials for this investigation. Supplementary materials would be:

- Computer with access to eCRFs

8. Risk – benefit analysis and ethical considerations

8.1. Risk-benefit analysis of the investigational device

A risk analysis according to ISO 14971 Application of risk management to medical devices has been conducted. Risks have been proven minimized or eliminated through appropriate design control, confirmed by pre-clinical bench, laboratory and clinical testing.

All unacceptable risks related to the device have been mitigated as far as possible and have been deemed acceptable for the clinical investigation. The Biatain Silicone Sacral Bandage is already CE marked.

8.2. Risk-benefit for subjects participating in the clinical investigation

The investigation is conducted in accordance with current law and applicable standards, see section 15. Statement of Compliance. The rights, safety and well-being of human subjects shall prevail over the interest of science of society.

Risks in this investigation are considered to be equal to the use of Silicone Sacral bandage products already on the market. Risks associated with the use of sacral bandage products are skin irritation and mechanical trauma. Please also see Adverse events, adverse device effects and device deficiencies section 18.

There is no known interaction between the use of the investigational device and the medication participants can take. Disadvantages of testing (trial engagement) may be the time spent on visits and responding to questions regarding baseline questions.

Possible benefits for the subjects in this investigation, are that subjects might have a lower risk of developing a pressure ulcer during hospitalization, which maybe will be beneficial for the subjects.

8.3. Risk Analysis for the conduct of the clinical investigation

A risk assessment of the clinical investigation will be conducted initially prior to the first subject enrolment and periodically re-assessed based on any new risks identified through the process. This assessment will be completed throughout the duration of the investigation, as defined by the study team. A risk-based monitoring strategy may be implemented including on-site remote, and central monitoring. Details of the strategy are defined in the monitoring plan.

8.4. Delegation of responsibility

Before initiation of the clinical investigation, sponsor must be provided with key personnel signed and dated curriculum vitae (not more than 2 years old) to verify their qualifications. Key site personnel are those, who treat or evaluate subject data in the clinical investigation. Also, the sponsor will ensure that all site personnel are trained in the investigation procedures, how to complete the CRFs, procedure for reporting an adverse

event or serious adverse event (how, when, to whom), and who to contact in case of emergency related to the investigational device.

9. Monitoring Plan

The sponsor is responsible for ensuring appropriate monitoring of the clinical investigation activities as described below.

The monitor will be the primary contact for the PI and healthcare delegates.

Monitoring activities are mandatory as per good clinical practice, however the extend and depth of these activities depend on the criticality of the clinical investigation, speed of enrolment, the experience of the Clinical investigation personnel in carrying out clinical investigations and specific investigation designs.

For the purpose of this clinical investigation the below described monitoring procedures have been determined.

9.1.1. Site selection visit

Depending on the prospective clinical investigation sites experience with the specific investigational device, an on-site qualification or site selection visit shall be performed during which, the feasibility of the clinical investigation requirements will be discussed and common agreement between sponsor and Principal Investigator shall be reached. This visit may also be replaced by one or more phone calls if the Principal Investigator is known to the sponsor.

9.1.2. Initiation visit

An initiation visit with full training on all aspects of the clinical investigation will be provided. The initiation visit will be held as a physical meeting or remotely using Microsoft Teams, Skype or Face Time and the visit will be held as close to investigation start as possible.

9.1.3. Monitoring visit(s)

The sponsor shall determine the extent and nature of monitoring appropriate for the clinical investigation based on the risk assessment. The sponsor shall ensure, through oversight of the clinical investigation and timely adverse event reporting, that unanticipated adverse device effects are identified and investigated rapidly so that, where necessary, additional risk control measures can be implemented.

The dedicated monitor is to ensure adherence to the clinical investigation plan, the safety of the subjects, accurate data recording on the eCRFs and to monitor recruitment rates and adherence to follow-up schedules. During the clinical investigation, monitors shall check that appropriate written informed consents have been obtained. The Principal Investigator shall permit and assist the monitor to carry out verification of completed e-CRFs against data in the source documents.

The Principal Investigator can delegate tasks to his collaborators, however the roles and responsibilities as time period of involvement for each clinical investigation personnel must be documented on the Site Personnel signature and Delegation list as well as training received before getting involved with the clinical investigation must be documented in the Clinical Investigation Training Log.

The monitor shall inform the sponsor about any problems relating to facilities, technical equipment, or medical staff involved in the clinical investigation. The monitor shall also be responsible for notifying such deficiencies in writing to the Principal Investigator and convene with the clinical investigation personnel appropriate and timely corrective actions.

The sponsor, or delegate, will provide clinical monitoring, including review of eCRF with verification to the source documentation, as defined in the monitoring plan.

The monitor shall make written reports to the sponsor, including documentation of any deviations after each visit and provide written follow up action items if any, to the Principal Investigator and/or clinical investigation personnel.

Source data verification will be performed to the extent it is possible. The Source Data Specification Form must be completed at the initiation visit detailing the location of the source data for each data point. Where no source data (besides the eCRF) is available the contents of the eCRF will be monitored.

The informed Consent Form and AE/ADE/DD will be 100% monitored for timely completeness.

Only the sponsor representatives will have access to all the eCRF's.

9.2. Source data verification

Source data is all information in original records, certified copies of original records of clinical findings, observations, or other activities in the clinical investigation, necessary for the reconstruction and evaluation of the clinical investigation. This includes source data initially recorded in an electronic format.

All documents and data related to the clinical investigation handled by site personnel, shall be produced and maintained in a way that assures reliability, integrity, control and traceability, and shall be appropriately stored to provide a complete history.

The Principal Investigator shall assure the accuracy, attribution, completeness, legibility and timeliness of the data reported to the sponsor in the eCRFs and in all required reports. All printed copies of electronic source documents shall be certified, as indicated by a dated signature by the investigational site personnel at the time the document is printed. Special requirements should be applied to the capture, review and retention of electronic source data, to ensure reliability, quality, integrity and traceability.

The data reported in the eCRFs shall be derived from source documents and be consistent with these source documents, and any discrepancies shall be explained in writing. The eCRF can serve as the source document and this must be documented on the Source Data Specification Form. The Source Data Specification Form must be completed at the initiation visit detailing the location of the source data for each data point agreed upon by the Principal Investigator.

10. Statistical considerations

10.1. Statistical design, method and analytical procedures

Definition of analysis populations

Safety populations and Intention to Treat (ITT) will be defined at a formal data review meeting before database lock. As a minimum, the data manager, the clinical manager and the statistician will be involved in the classification of subjects.

The safety population will be constituted by all subjects with valid informed consent. The ITT population (full analysis set) will be constituted by all subjects with valid informed consent, who have been exposed to the Test Product, with information on at least one endpoint.

The summary of the primary and secondary endpoints will be based upon the safety population, whereas the statistical analysis of the exploratory endpoint will be based on the ITT population. Invalid individual data points may be omitted from analysis even though the corresponding subject is part of the ITT population. Any exclusion of data points will be documented.

A formal per protocol (PP) population is not planned due to the explorative nature of the investigation. Considering the data obtained it might be considered to make additional explorative analyses based on a subset of the ITT population.

Analysis of the endpoints and baseline data.

The endpoints as well as baseline assessments will be listed and summarized by descriptive statistics. The summaries will be made for relevant visits (baseline or V1-V8), separately.

Summary statistics for continuous variables are presented with N, Mean, SD (standard deviation), Median, Min and Max, where N denotes the number of subjects contributing with non-missing data. For discrete variables, summary statistics are presented with N and percentage, where percentage is based on the total number of subjects/observations with non-missing data.

The incidence rate (proportion) of hospital-acquired pressure injuries in hospital-admitted patients will be estimated based on the exploratory endpoint (pressure injuries: Yes/No). The proportion of completed subjects answering "Yes" will be calculated. By use of an exact test in the Binomial distribution a 95% confidence interval will be estimated for the proportion.

All statistical analysis will be performed with SAS (version 9.4/Enterprise Guide version 7.1).

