5.2. Primary endpoint

Number of Adverse Events

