6.6. Point of enrolment

A subject is considered enrolled in the investigation when the written Informed Consent is obtained. The expected duration for each subject is described in 5.1.

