7.1. Clinical investigation-related procedures

Screening Visit (V0), Day 0:

- Introduction to the investigation and review of Subject information Form
- Check of in- and exclusion criteria
- Informed Consent Form – ICF signed at Visit 0. If subject wishes to have time for consideration, it is possible and the ICF is signed at Visit 1 the following day
- Inclusion in investigation and allocation of subject number after ICF is signed

Baseline Visit (V1), Day 1:

- Introduction to the investigation and review of Subject information Form
- ICF signed (if not signed at Visit 0)
- Confirmation of inclusion and exclusion criteria if more than 24 hours has passed since Visit 0
- Collect baseline information:
 - Gender (male/female)
 - Age (at time of enrollment (years)
 - Height (cm)
 - Weight (kg)
 - Urinary incontinence (Y/N)
 - Faecal incontinence (Y/N)
 - Date and main reason for admission (e.g., diabetes mellitus, cardiovascular disease, renal disease, pulmonary disease, anaemia, trauma, other)
 - Skin inspection
 - Braden Scale Score
- Apply Biatain Silicone Bandage on the sacral area

Baseline 2-7, skin inspection, Day 2-7:

- Partial lift of test product and skin inspection for signs of non-blanchable erythema over bony prominence/sacral pressure injury over bony prominence

- Re-application of the test product
- Has there been a test product change (Y/N)?
 - if yes, please register what the cause of the change was (dressing soilage, weakened border, damp/saturated dressing, bulky foam, other)

Termination Visit 8, Day 8 or at the day of discharge/earlier termination date:

- Have signs of non-blanchable erythema over bony prominence/sacral pressure injury over bony prominence developed (Y/N)?
 - If yes, please specify stage of pressure injury (*Appendix 3*)
- Was there any non-compliance to the local pressure injury prevention guideline (Y/N)?
 - If yes, explain non-compliance
 - if yes, please include a summary in the comment page

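### The safety population is defined by consent alone, so never-dressed subjects and pre-application adverse events can enter the device-safety summaries; add an exposure condition and state the denominator

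*Combined protocol and SAP*

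**What the plan says.** Section 10.1 defines two sets. For safety: "The safety population will be constituted by all subjects with valid informed consent". For the exploratory analysis: "The ITT population (full analysis set) will be constituted by all subjects with valid informed consent, who have been exposed to the Test Product", with the further requirement of data on at least one endpoint. The same section assigns the endpoints: "The summary of the primary and secondary endpoints will be based upon the safety population", and the exploratory endpoint goes to the ITT set.

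The primary endpoint in section 5.2 is "Number of Adverse Events". The secondary endpoint in section 5.3 is likewise a number, of device deficiencies. Section 5.5 says both were chosen to examine the safety of the dressing.

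On timing, section 6.6 says: "A subject is considered enrolled in the investigation when the written Informed Consent is obtained". Section 7.1 lists, under the screening visit (V0), "Inclusion in investigation and allocation of subject number after ICF is signed". It allows the form to be signed at V0, or at V1 if the subject wants time to consider. The dressing is applied at V1. Under section 5.1, V0 and V1 fall on the same day or on following days. In Table 5 (section 7.2) the row "Review of AEs/ADEs/SAEs/SADEs" is blank at V0 and marked from V1 onwards.

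**The concern.** The endpoints meant to describe the safety of the dressing are summarised on the only analysis set that does not require anyone to have worn it. The exposure condition sits on the ITT set, where it protects only the exploratory endpoint.

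The gap can occur in practice. A subject may consent at V0, receive a subject number, and then withdraw (section 6.5), be discharged, or fail the eligibility check at V1 before any dressing is applied. That subject belongs to the safety set.

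Two things are at stake. The reported safety N may not be the number of people who used the device, so a per-subject percentage taken on it would be too low. And because adverse events are collected whatever their cause (section 18.1) and no onset rule ties them to application, an event between consent and application can count in the primary endpoint. This second problem also affects subjects who are dressed later: the V1 review can pick up an event that began before the dressing went on.

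**Working it through.** **1. Is there a figure in the plan to reproduce?** No. The plan gives no expected safety rate for the safety set, no interval for either safety endpoint, and no number of subjects expected to consent without being dressed. The only relevant figure is the planned enrolment of 67, with at least 50 completers (sections 6 and 10.2). I use 67 as stated. It does not follow from the stated 30% drop-out (50/0.70 = 71.4, so 72; 50/0.75 = 66.7 gives 67), but that is a separate matter and does not affect this point.

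**2. The two definitions side by side.**

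| | Safety set | ITT set |
|---|---|---|
| Valid consent | required | required |
| Dressing applied | not required | required |
| Data on at least one endpoint | not required | required |
| Used for | adverse events, device deficiencies | pressure injury (exploratory) |

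**3. Effect on counts.** Adding subjects to a set cannot lower a count. A never-dressed subject contributes no adverse device effect, so those counts and the deficiency counts are not diluted. The all-cause adverse event count rises by one for each reported event before application.

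**4. Effect on a per-subject percentage.** Let u be the number consented but never dressed (assumed; not in the documents), with 67 consented. If p is the percentage among dressed subjects, the percentage on all consented subjects is

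p × (67 − u)/67,

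so the relative understatement is u/67.

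| u (assumed) | Dressed | (67 − u)/67 | Relative understatement |
|---|---|---|---|
| 0 | 67 | 1.000 | none |
| 3 | 64 | 0.955 | 4% |
| 7 | 60 | 0.896 | 10% |
| 10 | 57 | 0.851 | 15% |
| 17 | 50 | 0.746 | 25% |

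The last row is an extreme: 67 − 50 = 17, as if every planned drop-out left before application. As an illustration with u = 7, six subjects with an adverse device effect are 6/60 = 10.0% of those dressed, but 6/67 = 9.0% of those consented.

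**5. If someone added an interval.** With zero events, the exact two-sided 95% upper limit is 1 − 0.025^(1/n): 5.36% for n = 67 and 5.96% for n = 60. This shows scale only, because the plan has no interval for the safety endpoints.

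**6. Who would lack a scheduled adverse event review?** Not every never-dressed subject. One who attends V1 and fails eligibility there has the V1 review. One who is discharged early should have a termination visit on the day of discharge (section 5.1), and Table 5 schedules a review at that visit. The clearest remaining case is a subject who consents at V0 and changes their mind before V1.

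**The case against.** The strongest reply is that the plan does not contain the quantity that would be diluted. Both safety endpoints are counts, section 10.4 sets no formal success criterion for safety, and the only planned confidence interval is for the exploratory endpoint, on the exposure-based set. This stands. A reader might infer that the primary and secondary results as planned are diluted, or that a safety interval is too narrow. The documents support neither.

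A reader might also infer that the bias always runs towards a safer-looking device. It does not: all-cause events before application raise the primary count.

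Second, section 10.1 bases percentages on non-missing data, which might drop a subject with no record from the denominator. That is possible, but the plan does not say whether the absence of an adverse event form means missing data or zero events. The same section reports discrete variables with percentages, and Table 6 in section 18.2 gives anticipated device effects as incidence percentages, so per-subject percentages are a likely form of reporting.

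Third, the gap may be narrow or empty. V0 and V1 can share a day, and Table 4 in section 6.4 places signing at V1, although section 7.1 and Table 5 place it at V0. This also stands, which is why the effect is stated only conditionally.

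Fourth, a data review meeting before database lock will classify subjects. That meeting applies the written criterion, which is consent alone. Adding an exposure condition there, in an open-label study, would be a choice made with the data in view.

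**Conclusion.** The definition should be changed. As written, the safety set can include people who never wore the dressing and events that began before it was applied, while the exposure condition protects only the exploratory endpoint.

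The consequence is conditional. Counts of device effects and deficiencies are unaffected. A per-subject percentage on all consented subjects would be understated by u/67, and the all-cause adverse event count could be raised by events before application. The size of either effect depends on numbers that the documents do not give and that may be zero.

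A reader might go further and conclude that never-dressed subjects as a group have no adverse event review. Table 5 together with section 5.1 shows that most routes out of the study still include one. With no safety criterion or interval at risk, this is a should-fix.

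**What to change.** In section 10.1, define the safety population as every subject with valid consent who had at least one Biatain Silicone Sacral dressing applied. Then:

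- name this set as the denominator for the summaries of adverse events, adverse device effects and device deficiencies, and count events with onset at or after first application;
- list separately any adverse event between consent and first application, and any deficiency found before application, for example while a dressing is being handled, so that no safety information is lost;
- report in the disposition table the number who consented but were never dressed.

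The cost is a few sentences in section 10.1 and one extra listing. The denominator may be slightly smaller, and any percentage correspondingly a little less precise. No change to visits, data collection or sample size is needed.

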5.3. Secondary Endpoint

Number of Device Deficiencies

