10.4. Pass/fail criteria

There will be no formal success criteria for safety in this PMCF investigation.

The estimate rate (proportion) of hospital-acquired pressure injuries in hospital-admitted patients with a 95% confidence interval must be comparable to the confidence proportion and interval of the results found by Mölnlycke (5.3% [2.3%; 10.1%])³.

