18.2. Adverse device effect

An adverse event, which is related to the use of the investigational medical device, is an adverse device effect, and should be marked as unlikely related, possible related, probable related or with causal relationship on the adverse event form.

The definition of an adverse device effect includes any event resulting from insufficiencies or inadequacies in the instruction for use, deployment, implantation, installation and operation, or any malfunction of the medical device, as well as any event resulting from use error or from intentional misuse of the device.

Table 6 lists anticipated adverse device effects that may occur, based on the IFU and their likely incidence rates based on adverse events reported in clinical studies⁴.

Table 6

ANTICIPATED ADE	INCIDENCE RATES
Local pressure injury/Erythema*	1-10%
Skin irritation/inflammation/itching	0.1 %-1%
Maceration and/or local fungus infection of the skin	0.01-0.1%
Pain	0.01-0.1%
Blistering	0.01-0.1%
Allergic skin reaction	Not known

* *Temporary redness/erythema upon removal of the sacral bandage is not considered an adverse device effect, however an abnormal development in intensity or duration should be considered as such.*

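### The primary and secondary safety endpoints get descriptive summaries only, with no confidence interval, so the safety result would carry no statement of precision

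*Combined protocol and SAP*

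**What the plan says.** Section 3.1 names one primary objective, to evaluate safety. The primary endpoint (section 5.2) is "Number of Adverse Events" and the secondary endpoint (section 5.3) is "Number of Device Deficiencies". Section 5.5 says both were chosen to examine safety.

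Section 10.1 treats them as follows.
- Population: "The summary of the primary and secondary endpoints will be based upon the safety population". That population is everyone with valid consent, whether or not a dressing was applied.
- Method: "The endpoints as well as baseline assessments will be listed and summarized by descriptive statistics".
- Content: "For discrete variables, summary statistics are presented with N and percentage". Continuous variables get N, mean, SD, median, minimum and maximum.

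For the exploratory pressure-injury proportion, the same section adds: "By use of an exact test in the Binomial distribution a 95% confidence interval will be estimated for the proportion".

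Section 10.4 states: "There will be no formal success criteria for safety in this PMCF investigation". Section 10.2 says that enrolling 67 subjects, with at least 50 completers, is sufficient to evaluate safety. It gives a precision argument for the exploratory endpoint only. Section 10.3 sets a two-sided 5% level, but nothing on the safety side uses it. Table 6 in section 18.2 lists anticipated device effects with "their likely incidence rates based on adverse events reported in clinical studies".

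**The concern.** With no comparator and no success criterion for safety, the study can answer its primary question only by estimation. An estimate from about 67 subjects needs a statement of how far the true rate could lie from it, and the plan provides none for its primary or secondary endpoint. It does accept the need for an exact interval around an uncommon yes/no outcome, because it plans one for pressure injury.

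This matters most for uncommon events. Among the Table 6 categories other than pressure injury/erythema, the highest anticipated band is 0.1% to 1% (skin irritation), so counts of zero or one are to be expected. A reported 0% or 1.5% does not show how much higher a rate the data still allow. A reader of the report, or of a later clinical evaluation that draws on it, would have to work this out alone.

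**Working it through.** **The plan's own figure.** There is none to reproduce for safety. The power statement in section 10.2 concerns the exploratory endpoint, and this point does not depend on it.

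**Inputs.**
- n = 67 enrolled (sections 6 and 10.2). I assume that all 67 are exposed. The plan does not say how many consenting subjects might never receive a dressing.
- n = 50 (the completer minimum) serves only as a pessimistic figure for the number exposed. It is not the safety denominator, because drop-outs stay in the safety population.
- Two-sided 95% level (section 10.3) and the exact binomial method (section 10.1).
- Table 6 bands: 0.1% to 1% for skin irritation; 0.01% to 0.1% for maceration/fungal infection, pain and blistering.

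**Measure.** Both endpoints are event counts, and one subject may contribute several events. A binomial interval applies only after recasting them as the number of subjects with at least one event.

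**Formulas.** For x = 0, the upper limit solves (1 − p)^n = 0.025, so p = 1 − 0.025^(1/n).
- n = 67: 1 − 0.025^(1/67) = 5.36%.
- n = 50: 1 − 0.025^(1/50) = 7.11%.

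For x = 1, the upper limit solves (1 − p)^n + n·p·(1 − p)^(n−1) = 0.025. For n = 67 this gives 8.04%; substituting p = 0.0804 returns 0.02496. In general the limits are beta quantiles: lower B(0.025; x, n−x+1), upper B(0.975; x+1, n−x).

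| Subjects with event | n = 67: estimate (exact 95% limits) | n = 50: estimate (exact 95% limits) |
|---|---|---|
| 0 | 0% (0 to 5.4%) | 0% (0 to 7.1%) |
| 1 | 1.5% (0.04 to 8.0%) | 2.0% (0.05 to 10.6%) |
| 2 | 3.0% (0.4 to 10.4%) | 4.0% (0.5 to 13.7%) |
| 3 | 4.5% (0.9 to 12.5%) | 6.0% (1.3 to 16.5%) |

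**Check on the count scale.** For zero events in total, the exact Poisson upper limit is −ln(0.025) = 3.69 events. Over 67 subjects this is 3.69/67 = 5.5 per 100 subjects, close to the binomial 5.4%.

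**Adverse events of any kind.** The documents give no expected rate. The widest case is a proportion of one half, where the approximate half-width is 1.96 × √(0.25/67) = 0.12. The interval would reach at most about 12 percentage points either side.

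**How often zero would occur.** P(0) = (1 − p)^67. At a true rate of 1% this is 0.99^67 = 51%; at 0.1% it is 0.999^67 = 94%. A zero count is thus an ordinary outcome across the skin-irritation band.

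**What the sample can say about Table 6.** After 0/67, the upper limit of 5.4% is more than 5 times the top of the skin-irritation band (5.4/1) and about 54 times the top of the three 0.01% to 0.1% bands (5.4/0.1). No interval from this sample could confirm those bands.

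**The case against.** **Descriptive safety reporting is normal in a single-arm post-market study.** This stands. No test, threshold or larger sample is called for; what is missing is precision around the summary.

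**The exploratory endpoint has a reason to carry the interval.** It is the quantity that sections 10.2 and 10.4 set against an outside figure, so giving it an interval is consistent. That explains why it has one, but not why the primary objective has none.

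**The endpoints count all adverse events, related or not, and device effects are only a subset.** This also stands. The plan defines no separate device-effect summary, so the intervals need a measure based on subjects with at least one event, and adverse events of any kind must be included.

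**Pressure injury is already covered.** Largely true: the exploratory endpoint records sacral pressure injury, including non-blanchable erythema (section 7.1), and has the exact interval. The gap concerns the other device effects and device deficiencies, together with adverse events overall.

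**Any reader can compute the interval from the counts.** This is true only if subject-level counts are reported. A total number of events does not give the number of subjects affected.

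**Two stronger readings are tempting.** A reader might infer that the plan will treat few or no events as proof of safety. No section says so: section 10.4 disclaims a safety criterion and section 20 requires a critical evaluation of all the data. A reader might also infer that the plan fails a comparison it owes against Table 6. No objective or analysis promises that comparison.

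**Conclusion.** The point holds as a gap in precision reporting. Section 10.1 gives the primary and secondary safety endpoints no interval, and no other section supplies one, although safety is the primary objective, has no success criterion and rests on a sample size that is only asserted to be adequate. With 67 exposed subjects, a given event seen in none is compatible with a true rate up to 5.4%, and one seen in a single subject with up to 8.0%. If only 50 were exposed, the limits would be 7.1% and 10.6%.

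These figures assume exact two-sided 95% limits, independent subjects and a measure based on subjects with at least one event. They do not show that the dressing is unsafe or that the planned summaries are wrong. This is a worthwhile and inexpensive improvement, not an error that invalidates the analysis.

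**What to change.** Keep the planned event counts and listings. Add to section 10.1 wording along these lines:

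*The number and proportion of subjects with at least one adverse event, at least one serious adverse event, at least one adverse device effect and at least one device deficiency will each be presented with an exact two-sided 95% confidence interval. The denominator for adverse device effects and device deficiencies will be the subjects exposed to the test product. The safety conclusion will quote the upper limits.*

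The exposed denominator matters because the safety population includes consenting subjects who may never have worn the dressing. Counting them would dilute device-related rates and lower the upper limits.

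Intervals by Table 6 category are optional and should be labelled descriptive: the sample cannot confirm the 0.01% to 0.1% bands, and sacral pressure injury already has its exploratory interval.

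The cost is a few lines using the exact method already planned. Endpoints, visits, data collection and sample size stay as they are. The one downside for the sponsor is that a zero or low count appears beside its upper limit and looks less favourable.
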